1.4 Protocol synopsis

Protocol Number and Title: BGI-20170204 Calorie Restriction Dietary Intervention

Meals: The Normal Calorie diet at baseline and Calorie Restriction diet during Calorie Restriction period.

Phase or Type of study: Interventional

Study Objectives: The purpose of this intervention study is to evaluate the effect of calorie restriction on BMI loss, amino acid, and gut microbiota in healthy volunteers of two different enterotypes and provide useful insights for potential application of gut microbiome stratification in personalized nutrition intervention.

Study design: The study included a one-week run-in period (baseline) and a three-week CR dietary intervention period.

Sample Size: 41 individuals (24 females and 17 males aged 30 ± 6 years old) completed the whole intervention.

Eligibility Criteria:

Recruited volunteers should meet all the following criteria:

- 1) BMI less than 28 kg/m^2 and more than 18 kg/m^2 ;
- 2) Without antibiotics in the recent 2 months;
- 3) Without prebiotic or probiotic supplements in the recent 2 months;
- 4) Without hypertension, diabetes mellitus, gastrointestinal disease and other severe auto-immune diseases;
- 5) Regular eating and lifestyle patterns;
- 6) No international travel in the recent 3 months;
- 7) Without prebiotic or probiotic supplements in the recent 2 months.

Volunteers meeting any of the following criteria will not be eligible to participate in this study:

- 1) With antibiotics in the recent 2 months;
- 2) Failure to comply with the experimental requirement;

2.1 Background

Calorie restriction (CR), which has the potential effect on weight loss and blood amino acids, has been demonstrated to associate with gut microbiota in human, especially in obese individuals [1, 2]. Observational studies with long-term CR found that CR resulted in weight loss and decreasing chronic disease risk factors in nonobese persons [3-6]. A 4week CR intervention improved gut barrier integrity, reduced systemic inflammation on gut microbial diversity and BMI loss in obese women, suggesting a potential association among gut microbiota, CR and BMI [7]. Enterotype, a concept for stratifying individuals based on the gut microbiota, was first described in 2011 and was closely linked to longterm dietary patterns [8, 9]. Plenty of studies have reported that individuals have shown microbial-dependent (enterotypes, *Bacteroides* to *Prevotella* ratio) metabolic responses to the same intervention, including changes of BMI and glycemic indices [9-14]. As for the association between CR and blood amino acids, Biolo et.al reported changes in blood amino acids of 9 healthy nonobese men after a 2-week CR diet [15]. Despite the plenty of studies on CR as we mentioned above, to our knowledge, there are no studies for simultaneously evaluating impacts of CR on BMI, gut microbiota and blood amino acids in nonobese individuals in a single study.

2.2 Description of population to be studied, enrollment targets

Volunteer-wanted posters were propagated at the China National Gene Bank in Shenzhen from March to April 2017. A non-obese healthy volunteer was considered if his/her BMI less than 28 kg/m² [16]. 50 individuals met all the criteria and were recruited in this study,

and 41 individuals (24 females and 17 males aged 30 ± 6 years old) completed the whole intervention (**Table 1**). In addition, recruited volunteers should meet all the following criteria: 1) without antibiotics in the recent 2 months; 2) without prebiotic or probiotic supplements in the recent 2 months; 3) without hypertension, diabetes mellitus, gastrointestinal disease and other severe auto-immune diseases; 4) regular eating and lifestyle patterns; 5) no international travel in the recent 3 month; 6) without prebiotic or probiotic supplements in the recent 2 months. The study was approved by the institutional review board on bioethics and biosafety of BGI-Shenzhen, Shenzhen (NO. BGI-IRB 17020). All participates were fully informed of the design and purpose of this intervention study and signed a written informed consent letter.

Table 1. Cohort Description		
	Cohort	
	(Mean ± SD)	
Number of subjects	41	
Sex (female/male)	24/17	
Age	30 ± 6	
BMI (kg/m ²)	23.72 ± 2.81	
Weight(kg)	64.84± 11.57	

2.3 Study duration

During the first week (run-in period), all healthy volunteers consumed their usual diet and were encouraged to avoid yogurt, high-fat foods and alcohol. The CR diet was comprised of ~50% calories of a normal-calorie diet (female, 1000kcal/day; male, 1200kcal/day). It was designed with carbohydrate, fat and protein as approximately 55%, 30% and 15% of the total energy intake respectively, according to the Dietary Guidelines for Chinese

Residents (2016) and nutritionally balanced [17] and a recent large nutritional study in China [18]. Common foods in low-calorie diets such as rice, vegetables, eggs, pork and beef were prepared in this study center to control experimental variables introduced by different foods and calorie estimation errors. Traditional Chinese cooking style - boiled, stir-fried and stewed, were applied for foods. For each meal, digital scales were used to measure the nutritional and caloric values of different foods and total meals for male and female respectively. BMI, blood and fecal samples of each volunteer were collected at this study center at baseline and after the 3-week CR intervention (**Figure 1**). BMI, blood and fecal samples of each volunteer at baseline and after the 3-week CR intervention (**Figure 1**).

[figure not shown]

Figure 1. Overview of the experimental design. Illustration of experimental design, including a 1-week run-in period (baseline) and a 3-week calorie restriction (CR) dietary intervention trial with 50% energy deficit diet (male, ~1200Kcal/day; female, ~1000Kcal/day). BMI, fasting blood samples and fecal samples of 41 enrolled healthy subjects were collected before and after the CR intervention to assess its effects on BMI, blood amino acids and gut microbiome in two enterotype groups.

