5.1 Detailed study procedures

5.1.1 Screening information

Screening information			
Step	Descriptor	Details	Appendix
1	Statement of Informed Consent	Each participate must read, understand and sign the Statement of Informed Consent before enrolled in the study. The Principal Investigator or designer conducting the informed consent discussion must sign the consent form. Note: the participate must be provided with a signed copy of this document.	
2	Demographics	Age, sex, height, weight, body mass index	
3	Healthy history	Record the participates' dietary and medical and international travel history	
4	Eligibility at screening	All responses to Inclusion Criteria questions must be answered "yes", and all responses to Exclusion Criteria questions must be answered "no" for the participate to be considered eligible	

5.1.2 Baseline period for recruiting participates.

Baseline information				
Step	Descriptor	Details	Appendix	
1	Baseline clue	Participate will complete the baseline clue measures regarding their own contact dietary habits.	exclude 9 participates	
2	BMI clue	Record participates' BMI.		
3	Measuring BMI	BMI was measured via the clinic scale.		
4	Collecting Fasting blood samples	Fasting blood samples were collected at the end of baseline for extracting amino acids	5 participates without fasting blood	

5	Collecting fecal samples	Fecal samples were self-collected and then transferred to the laboratory on dry ice and kept frozen at -80°C at baseline.	
6	Eligibility after Baseline Examination	All responses to Inclusion Criteria questions must be answered "yes", and all responses to Exclusion Criteria questions must be answered "no" for the participate to be considered eligible.	

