6.1 Statistical methods to be employed

All outcomes will be presented using descriptive statistics: Wilcoxon rank-sum test is used to detect the significant differences on phenotypes, the concentrations of blood amino acids and the relative abundances of genera and species between enterotypes. Wilcoxon signedrank test is used to detect the significant differences on phenotypes, the concentrations of blood amino acids and the relative abundances of genera and species in paired samples before and after the intervention. Permutational multivariate analysis of variance (PERMANOVA) is used to detect the association between enterotypes and the overall blood amino acid profile at baseline by using PERMANOVA with 9,999 permutations on enterotypes. Principal coordinate analysis is used to visual overall gut microbial based on the relative abundance profiles between baseline and after the intervention. Principal component analysis is used to visual overall amino acid composition based on the blood amino acid profiles between baseline and after the intervention. To investigate whether we could predict BMI loss ratio using omics features, we will perform a Lasso (Least absolute shrinkage and selection operator) regression analysis between baseline relative abundances of gut common species and the concentrations of blood amino acids (independent variables), and BMI loss ratio (dependent variables). We first normalize values of both independent and dependent variables (R, scale function). We then use the R function cv.glmnet to choose the most appropriate value for λ in the Lasso model (R glmnet package, alpha =1, family="gaussian", nfolds=10, alpha=1, nlambda=100). Here, λ is the tuning parameter ($\lambda > 0$) which controls the strength of the shrinkage of the variables. We then apply the Lasso feature selection process by shrinking the Lasso regression coefficients of non-informative variables to zero and selecting the variables of non-zero coefficients. To reduce overfitting with a limited sample size (n=41), we apply leave-one-out cross validation (LOOCV) to estimate the prediction performance of BMI loss ratio using a generalized linear model (GLM) of the selected features (creatFolds function in R caret package and the glm function in R base package). Likewise, we also use baseline BMI values for LOOCV to estimate its prediction performance for CR-associated BMI loss ratio. Spearman's rho values will be calculated between actual BMI loss ratios and the predicted values. P-value adjustment is applied for multiple hypothesis testing on the concentrations

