#### 6. Analyses

All outcomes will be presented using descriptive statistics: Wilcoxon rank-sum test is used to detect the significant differences on phenotypes, the concentrations of blood amino acids and the relative abundances of genera and species between enterotypes. Wilcoxon signedrank test is used to detect the significant differences on phenotypes, the concentrations of blood amino acids and the relative abundances of genera and species in paired samples before and after the intervention. Permutational multivariate analysis of variance (PERMANOVA) is used to detect the association between enterotypes and the overall blood amino acid profile at baseline by using PERMANOVA with 9,999 permutations on enterotypes. Principal coordinate analysis is used to visual overall gut microbial based on the relative abundance profiles between baseline and after the intervention. Principal component analysis is used to visual overall amino acid composition based on the blood amino acid profiles between baseline and after the intervention. To investigate whether we could predict BMI loss ratio using omics features, we will perform a Lasso (Least absolute shrinkage and selection operator) regression analysis between baseline relative abundances of gut common species and the concentrations of blood amino acids (independent variables), and BMI loss ratio (dependent variables). We first normalize values of both independent and dependent variables (R, scale function). We then use the R function cv.glmnet to choose the most appropriate value for  $\lambda$  in the Lasso model (R glmnet package, alpha =1, family="gaussian", nfolds=10, alpha=1, nlambda=100). Here,  $\lambda$  is the tuning parameter ( $\lambda > 0$ ) which controls the strength of the shrinkage of the variables. We then apply the Lasso feature selection process by shrinking the Lasso regression coefficients of non-informative variables to zero and selecting the variables of non-zero coefficients. To reduce overfitting with a limited sample size (n=41), we apply leave-one-out cross

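### Intake is fixed by sex, but neither the enterotype comparison nor the omics prediction model accounts for sex and body size, so added value beyond them cannot be shown

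*Protocol*

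**What the plan says.** **Intake.** The text of Protocol 2.3 states: "The CR diet was comprised of ~50% calories of a normal-calorie diet (female, 1000kcal/day; male, 1200kcal/day". Figure 1 in the same section calls this a "50% energy deficit diet (male, ~1200Kcal/day; female, ~1000Kcal/day". SAP section 2 repeats both descriptions. Meals were weighed out as "total meals for male and female respectively". Nothing in either document scales intake to the individual.

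**Prediction.** The Lasso relates "baseline relative abundances of gut common species and the concentrations of blood amino acids (independent variables), and BMI loss ratio (dependent variables" (SAP section 6; same in Protocol 6.1). Performance is then estimated by LOOCV "using a generalized linear model (GLM) of the selected features". The comparator is a separate model: "Likewise, we also use baseline BMI values for LOOCV to estimate its prediction performance for CR-associated BMI loss ratio".

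**Enterotype comparison.** Protocol 4.1 lists the difference in BMI change between enterotypes (28 v 13) as the second of two primary outcomes. Protocol 6.1 and SAP section 6 assign between-enterotype comparisons to the Wilcoxon rank-sum test, with no covariates.

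**Available covariates.** Protocol 5.1.1 records "Age, sex, height, weight, body mass index" at screening. The cohort is "41 individuals (24 females and 17 males aged 30 ± 6 years old".

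**The concern.** Sex determines the prescribed intake. At a given intake, body size determines how large that intake is relative to need. Both are therefore plausible determinants of BMI loss, and both may also be related to serum amino acids, gut species or enterotype. Enterotype is an observed characteristic, not a randomised one, so nothing in the design balances sex or size across the 28 and the 13.

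The study's stated purpose is to inform microbiome stratification in personalised nutrition. That requires knowing whether enterotype or omics data tell us more than sex and body size already do. No planned analysis asks this. An omics feature could be selected because it stands in for sex or size, and an enterotype difference could be created or hidden by a different mix of men and women. The reader of the results could not tell.

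**Working it through.** **The plan's own figure.** The only sample-size figure (SAP 2.1) is for the overall BMI change. With dz = 0.5, two-sided alpha 0.05 and Wilcoxon efficiency 3/π, n = 35 gives power 0.80, and 35/(1 − 0.30) = 50. Both reproduce. No figure is given for the enterotype comparison or the prediction model, so the steps below rest on stated assumptions.

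**1. Which terms enter which analysis**

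| Analysis | Sex | Size measure | Omics or enterotype |
|---|---|---|---|
| Lasso and its GLM | no | no | species, amino acids |
| Comparator LOOCV | no | baseline BMI | no |
| Enterotype rank-sum test | no | no | enterotype |

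No row combines sex or size with omics or enterotype.

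**2. How the relative deficit varies.** Deficit = 1 − intake/(k × weight). Intake is from Protocol 2.3. Weight is 64.84 ± 11.57 kg from Table 1, so mean ± 1 SD is 53.3, 64.8 and 76.4 kg. The need k (kcal/kg/day) is not in the documents and is assumed to be 28 to 37, the same for both sexes. Example: a woman at 64.84 kg with k = 31 has 1 − 1000/(31 × 64.84) = 1 − 1000/2010 = 50.2%.

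| k = 31 | 53.3 kg | 64.8 kg | 76.4 kg |
|---|---|---|---|
| Women, 1000 kcal | 39.4% | 50.2% | 57.8% |
| Men, 1200 kcal | 27.3% | 40.3% | 49.3% |

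Over k = 28 to 37 the range is 33.0–64.6% for women and 19.5–57.6% for men. Table 1 pools the sexes, so these weights are only illustrative within sex, but any constant k gives a gradient with size.

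**3. Does sex itself shift the mean deficit?** Suppose men weigh 1.2 times as much as women (assumed). Then (24w + 17 × 1.2w)/41 = 64.84, so 44.4w = 2658.44, giving w = 59.9 kg for women and 71.8 kg for men. At k = 30 both sexes have a mean deficit of 44%; at k = 35 both have 52%. With ratios of 1.1 to 1.3 the sexes differ by about 4–5 points, in either direction. Most of the spread comes from size within sex.

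**4. A feature that only tracks sex.** Simulation with 24 women and 17 men; the feature has no link to BMI loss given sex. The table shows the chance of p<0.05 for feature against outcome. All correlations are assumed.

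| Sex–outcome r | Sex–feature r = 0.3 | 0.5 | 0.7 |
|---|---|---|---|
| 0 | 5% | 5% | 5% |
| 0.3 | 9% | 15% | 27% |
| 0.5 | 16% | 36% | 66% |

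With sex adjusted for, every cell is about 5%.

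**5. The same through a Lasso.** 40 features, 10 of them correlated 0.5 with sex, 10-fold cross-validation, 40 replicates per setting (so imprecise). Selection of sex-tracking v other features was 7% v 6% at sex–outcome r = 0, 14% v 12% at 0.3, and 27% v 12% at 0.5. At 0.5 with sex forced in, it was 9.5% v 12%.

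**6. The enterotype test.** Simulation of 28 v 13 with 17 men in all and no enterotype effect, the sexes differing by 0.8–1.0 SD in BMI loss (assumed). If 9 of the 13 Prevotella volunteers were men, the rank-sum test rejected 11–17% of the time at a nominal 5%. If 7 of 13 were men, it stayed near 5%. The documents do not give sex by enterotype.

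**The case against.** Several points on the other side are sound.

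- A reader might infer that the comparator ignores body size. It does not: baseline BMI is a size measure. What it lacks is sex and weight, and because it is a separate model it gives a side-by-side comparison of Spearman's rho, not an adjustment.
- A reader might infer that each volunteer was meant to receive 50% of personal need. The text sets the 50% against a normal-calorie diet and never promises that. Figure 1's caption is looser, which calls for reconciliation and no more.
- Sex-specific intake may largely offset sex differences in need (step 3), so a strong effect of sex on loss cannot be presumed.
- The Lasso's stated aim is prediction, and a proxy for sex can still predict. The Lasso is also in neither outcome list in Protocol 4.1.
- Imbalance between enterotypes is not shown. The planned rank-sum tests on phenotypes, a term left undefined, might cover baseline BMI or weight.

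These points limit the size and certainty of the concern. They leave its core: no analysis tests omics or enterotype over and above sex and size. For the enterotype question this touches a primary outcome. Testing phenotypes for baseline differences, even if it is done, does not adjust the comparison.

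**Conclusion.** The point holds as a gap in what the plan can show. Intake has two levels set by sex, the relative deficit varies with size, and the plan cannot separate enterotype or omics effects from sex and body size.

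A reader might go further and infer that selected features or an enterotype difference would be artefacts of sex. The documents do not support that. It would need sex or size to be related both to BMI loss and to the features or enterotype, and neither relation is reported. Under the assumed correlations the effect runs from nil (sex unrelated to loss) to large (36–66% nominal association at sex–outcome r = 0.5 with sex–feature r of 0.5–0.7). At sex–outcome r = 0.3 the excess in Lasso selection was small, 14% v 12%. The harm is to the interpretation of features and enterotype as markers of response more than to predictive accuracy. The remedy is cheap and worth making.

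**What to change.** 1. **Enterotype comparison.** Alongside the planned rank-sum test, test the difference in BMI change with a linear model (rank-based if preferred) adjusted for sex and baseline BMI. Tabulate sex, weight and BMI by enterotype.
2. **Prediction.** Make the comparator sex plus baseline BMI (or weight). Fit the same model plus omics with those terms unpenalised (`penalty.factor=0` in glmnet), on the same volunteers (36 where amino acids are used). Repeat selection inside each LOOCV fold, because selecting once on all the data would flatter the increment. Report the increment in addition to the planned omics-only performance.
3. **Wording.** Reconcile the two descriptions of the 50% in Protocol 2.3 and SAP section 2. This takes no position on the diet itself.

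**Cost.** Two degrees of freedom in a small sample and a little more analysis. Sex, weight and BMI are already recorded, so no new data are needed.

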3.1 Description of objectives and purpose

The purpose of this intervention study is to evaluate the effect of calorie restriction on BMI

loss, amino acid, and gut microbiota in healthy volunteers of two different enterotypes and provide useful insights for potential application of gut microbiome stratification in personalized nutrition intervention.

4.1 Primary and secondary outcomes

The primary outcomes for this study are:

- Change in BMI of all volunteers (n=41) following calorie restriction dietary intervention
- Different changes in BMI between enterotypes *Bacteroides* (n=28) and enterotypes *Prevotella* (n=13) following calorie restriction dietary intervention

BMI was measured via the clinic scale. To avoid intra-individual variations, BMI was collected multiple times of each volunteer during the last week of the CR intervention, and the averaged BMI value was used as his/her after-intervention BMI.

The secondary outcomes for this study are:

- Change in the concentration of 31 blood amino acids of 36 volunteers following calorie restriction dietary intervention
- Different in the concentration of 31 blood amino acids between enterotypes *Bacteroides* (n=25) and enterotypes *Prevotella* (n=11) following calorie restriction dietary intervention
- Change in the gut microbiota of all the volunteers (n=41) following calorie restriction dietary intervention
- Different in the gut microbiota of between enterotypes *Bacteroides* (n=28) and enterotypes *Prevotella* (n=13) following calorie restriction dietary intervention

The concentrations of 31 amino acids and derivatives in the fasting serum samples were measured by LC-MS/MS. Fasting blood samples were collected before and after the

intervention for amino acid analysis. These blood samples were then centrifuged, and serum samples were collected and stored at -80 °C. The concentrations of 31 amino acids and derivatives in the serum samples were then measured via ultra-high pressure liquid chromatography (UHPLC) coupled to an AB Sciex Qtrap 5500 mass spectrometry (AB Sciex, US) as described previously [19].

The gut microbial composition was determined using shotgun metagenomics sequencing of fecal DNA. Fecal samples were self-collected and then transferred to the laboratory on dry ice and kept frozen at -80°C before and after the CR intervention. Fecal DNA was extracted following a manual protocol as described previously [20]. The DNA concentration was estimated by Qubit (Invitrogen). Library construction and shotgun metagenomic sequencing were performed on qualified DNA samples based on the BGISEQ-500 protocol in the single-end 100bp mode [21]. Raw reads of BGISEQ-500 with SE100 mode were trimmed by an overall accuracy (OA) control strategy to control quality [21]. After trimming, averagely, 98.15% of the raw reads remained as high-quality reads. By using SOAP2.22 software, the high-quality reads were aligned to hg19 to remove reads from host DNA (identity ≥ 0.9). The retained clean reads were aligned to the integrated non-redundant gene catalog (IGC) using SOAP2.22 [22] and the average mapping rate and unique mapping rate were 80.18% and 65.76% respectively (identity ≥ 0.95). The relative abundance profiles of genes, genera, species and Kyoto Encyclopedia of Genes and Genomes orthologous groups (KEGG, KOs) of each sample were calculated by summing the relative abundances of their assigned IGC genes [22].

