# 3. Aims and objectives

The purpose of this intervention study is to evaluate the effect of calorie restriction on BMI loss, amino acid, and gut microbiota in healthy volunteers of two different enterotypes and provide useful insights for potential application of gut microbiome stratification in personalized nutrition intervention.

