validation (LOOCV) to estimate the prediction performance of BMI loss ratio using a generalized linear model (GLM) of the selected features (creatFolds function in R caret package and the glm function in R base package). Likewise, we also use baseline BMI values for LOOCV to estimate its prediction performance for CR-associated BMI loss ratio. Spearman's rho values will be calculated between actual BMI loss ratios and the predicted values. P-value adjustment is applied for multiple hypothesis testing on the concentrations of blood amino acids, the relative abundances of gut microbial genera and species use Benjamini-Hochberg (BH) method. R 3.5.0 will be used for all statistical analysis.

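### For amino acids and gut taxa the between-enterotype test is not defined on change; followed as written it compares levels, which cannot show a different response to calorie restriction

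*Protocol*

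**What the plan says.** Protocol 4.1 has three between-enterotype outcomes. The BMI one, which is primary, is worded "Different changes in BMI between enterotypes". The two secondary ones drop the reference to change: "Different in the concentration of 31 blood amino acids between enterotypes" and "Different in the gut microbiota of between enterotypes". All three end with a phrase that places them after the CR diet. The matching whole-group outcomes for BMI, amino acids and microbiota are all worded as changes.

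Protocol 6.1 and SAP 6 carry the same methods text. The rank-sum test covers phenotypes, amino-acid concentrations and "the relative abundances of genera and species between enterotypes". The signed-rank test covers the same variables, ending with "the relative abundances of genera and species in paired samples before and after the intervention". The only enterotype analysis with a stated time point is the PERMANOVA of the amino-acid profile, at baseline. On multiplicity, "P-value adjustment is applied for multiple hypothesis testing on the concentrations of blood amino acids" and on genera and species, by the BH method.

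SAP 4.2 gives the two sampling times but no between-enterotype contrast. Neither document says how enterotype is assigned, or from which sample.

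**The concern.** The purpose of sampling twice is given in the Figure 1 caption (Protocol 2.3): "to assess its effects on BMI, blood amino acids and gut microbiome in two enterotype groups". SAP 3 looks ahead to "potential application of gut microbiome stratification in personalized nutrition intervention". Both concern response to the diet. Stratifying by enterotype is useful if the enterotypes respond differently, not merely if they differ.

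A rank-sum test on levels answers another question. If the enterotypes already differ in an amino acid and CR moves both equally, the post-CR levels still differ and could be read as a response. If CR closes a baseline gap, the post-CR levels agree and a real differential response is missed. The signed-rank test does use within-person change, but it does not compare enterotypes; significance in one enterotype and not in the other is not a test of the difference.

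The point is sharpest for taxa. The groups are named for *Bacteroides* and *Prevotella*, so those genera would be expected to differ before any diet.

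**Working it through.** **1. The plan's own figures.** The only design calculation (SAP 2.1) gives 35 evaluable participants for the whole-group BMI change, and 35/(1 - 0.30) = 50 recruited. It reproduces but does not bear on these comparisons. From the documents I use the group sizes in Protocol 4.1 (25 v 11 for amino acids, 28 v 13 for taxa) and two-sided alpha 0.05. The baseline gap, the before-after correlation r and the distributions are not in the documents; they are assumptions, varied below.

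**2. What each analysis estimates.** Let d be the baseline gap between enterotypes, δ the difference in change (both in SDs), with SD 1 at each visit.

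- Post-CR levels: expected difference d + δ.
- Change: expected difference δ; variance of a change 2(1 - r).
- Baseline-adjusted: expected coefficient (d + δ) - r·d = δ + (1 - r)d.

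With d = 0.5 and δ = 0, levels estimate 0.5 and change estimates 0; adjustment estimates 0.15 at r = 0.7. With d = 0.5 and δ = -0.5, levels estimate 0 and change -0.5. Only change isolates δ when a stable gap exists.

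**3. Amino acids, 25 v 11, before BH.** Simulated rejection rates; lists run over r = 0.5, 0.7, 0.9.

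| Scenario | Levels | Change |
|---|---|---|
| No gap, no differential response | 4-5% | 4-5% |
| Stable gap 0.3 SD | 11-12% | 4-5% |
| Stable gap 0.5 SD | about 24% | 4-5% |
| Stable gap 0.8 SD | 53-54% | 4-5% |
| Gap 0.5 SD closed by CR | 4-5% | 25, 38, 82% |

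Baseline adjustment under a stable 0.5 SD gap rejects 11, 8, 6%.

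**4. After BH over 31 analytes** (r = 0.7; 5 to 31 analytes differing; inter-analyte correlation 0 or 0.3). Per differing analyte, levels reject 0.6-1.5%, 2.5-7.2% and 12-37% at gaps of 0.3, 0.5 and 0.8 SD; change rejects 0.1-0.2%.

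**5. The scale of change matters.** If CR multiplies every value by a common factor f, raw change is about (f - 1) × baseline, so it is larger where baseline is higher. With log SD 0.25 and a 0.8 SD gap, the ratio of group means is exp(0.8 × 0.25) = 1.22. A common 30% fall then gives mean changes of -0.30 and -0.30 × 1.22 = -0.37, in units of the lower group's baseline mean. For falls of 20-30% and r = 0.7-0.9, rank-sum on raw change rejects 8-23%; on log change, 4-5%.

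**6. Amino acids linked to the defining genus.** If enterotype comes from the baseline sample and an amino acid correlates 0.3-0.5 with that genus through person effect and visit noise, change rejects 6-18% and adjustment 5% (r = 0.5-0.9).

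**7. Taxa, 28 v 13, no CR effect.** The assignment rules here are illustrative; lists run over r = 0.5, 0.7, 0.9.

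- *Defining genus, groups = top 13 of 41 on the baseline sample.* Levels reject 68, 97, 100%. Change rejects about 70, 45, 18%, from regression to the mean. Adjustment rejects 5% on a normal scale and 5-6% on ranks, but 17, 23, 27% on raw log-normal abundance.
- *Same genus, groups formed on the mean of both samples.* Change rejects 5%; adjustment 94, 79, 36%.
- *Another taxon correlated 0.5 with that genus, baseline rule.* If visit noise is shared: change 20, 14, 8%, adjusted 5%. If the link is only through stable person effects: change 5%, adjusted 32, 19, 9%. The 32% is a boundary case, since it needs a person-effect correlation of 0.5/0.5 = 1.

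**The case against.** The best defence is that the methods sentence lists variables and does not fix their scale. It names phenotypes without mentioning change, although the BMI outcome is explicitly about changes. Each secondary between-enterotype bullet also follows a bullet about change and shares its closing phrase. A change comparison in loose English is a fair reading, and that stands. A reader might infer that the investigators chose to test levels, or that they will report level differences as response to CR; the documents say neither. What they do not do is state the contrast, so two analysts could run different tests from the same plan.

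The objectives can also be read as asking for the effect of CR within each enterotype, which signed-rank tests could address. That would not support the outcomes in Protocol 4.1 that set one enterotype against the other.

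A reader might further take the unadjusted 24% or 53-54% as expected false-finding rates. They are not. BH is planned, and at gaps of 0.3-0.5 SD it brings the rate per differing amino acid to single figures. Nor are the level differences necessarily false: they may be real, and the error would lie in calling them a response.

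Finally, change scores are no universal remedy. Steps 5 to 7 bear this out, and the fix is limited accordingly.

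**Conclusion.** The concern holds, with limits. The between-enterotype contrast for amino acids and taxa is not defined on change, and the test as written compares levels, which cannot show a differential response to CR. The primary BMI outcome is worded as changes, so only secondary outcomes are affected. The plan should be corrected.

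The size is illustrative. With a stable 0.5 SD gap at 25 v 11, levels reject about 24% before BH against 4-5% for change; after BH, 2.5-7.2% per differing amino acid, and 12-37% at 0.8 SD. These figures rest on assumed gaps, correlations and normal data. That levels test d + δ and not δ needs none of those assumptions. For the defining taxa, the appropriate analysis cannot be settled until the assignment rule is stated.

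**What to change.** - **Amino acids.** Define the outcome as the between-enterotype difference in within-person log change, log(after/before). Test it by rank-sum with BH over the 31 analytes. Add a baseline-adjusted sensitivity analysis on the log scale. Do not use raw differences unless an additive common effect can be defended.
- **Taxa.** State how, and from which sample, enterotype is assigned. Do not use post-CR levels as evidence of a differential response. For taxa that define the enterotype, if assignment uses only the baseline sample, do not rely on change scores: adjust for baseline on ranks or logs, or report descriptively. If the post-CR sample enters the assignment, report them descriptively. For other taxa, name one primary analysis in advance and report the other as sensitivity.
- **Levels.** Label any between-enterotype test of levels, with its time point, as a description of the groups.

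Cost: outcome and SAP wording, an assignment rule and some further analyses; no new data. Change has less power than levels when r is below 0.5, because 2(1 - r) then exceeds 1. For a true 0.5 SD differential change with no gap at 25 v 11, change v levels is 18 v 24% at r = 0.3, 24 v 24% at 0.5 and 37 v 24% at 0.7. Baseline adjustment does better in that no-gap case (33% at r = 0.5, 46% at 0.7). Primary and sensitivity results may disagree, and inference on the defining taxa may be lost. The documents already report completers, enterotype counts and missing blood data, so the amendment should be dated, and labelled post hoc if results have been seen.
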